1.0 Background and Rationale

Ultrasound is a fundamental diagnostic tool in Obstetrics in both resource-rich and resource-limited settings. One barrier to sustainable ultrasound use in low-resource settings is access to the necessary consumable goods, specifically ultrasound gel, to serve as the coupling medium required to conduct the sound waves between the ultrasound probe and the patient's tissue to produce quality images. In low-resource settings, unreliable access to commercial ultrasound gel and its high cost can limit routine use of ultrasonography.

Coconut oil is a low cost and widely available alternative to commercial ultrasound gel that additionally has been shown to be moisturizing, antibacterial, anti-inflammatory, and safe. There are no studies to date that compare the quality of ultrasound images obtained using coconut oil and commercial ultrasound gel. There are also no studies that evaluate patient satisfaction with the use of coconut oil as a coupling medium for OB ultrasounds.

Coconut oil is isolated from the kernel or meat of mature coconuts harvested from the coconut palm (*Cocos nucifera*). It has been shown to be as effective as mineral oil as a moisturizer to treat mild to moderate xerosis [1], however, it has the additional benefit of being antiseptic. Coconut oil is made up of medium-chain fatty acids which are effective in destroying lipid-coated bacteria [2]. Studies have shown that lauric acid is the most inhibitory saturated fatty acid against gram-positive organisms such as the streptococcus and staphylococcus species that are the most common causes of bacterial skin infections. Coconut oil happens to be the highest natural source of lauric acid, making up almost 50% of coconut's fat content [3]. Cellular studies have also shown that monoglyceride derivatives of lauric acid exhibit antiviral and antifungal activity [4]. Additionally, coconut oil increases the expression of skin barrier molecules and collagen, enhancing skin's barrier function and improving hydration by preventing water evaporation [5]. The annual average cost of coconut oil in 2020 per the World Bank Commodities Price Data was 1,010 USD/mt which can be converted to 0.0010 USD/g or 0.02 USD/20g [6]. At Indiana University Hospitals, the standard ultrasound gel used, Aquasonic 100 (Parker Laboratories, Inc., Fairfield, NJ), is sold in 20g packets for 0.34 USD. Therefore, the standard ultrasound gel used at Indiana University Hospitals is 17 times more expensive than coconut oil by weight. Of the world's 195 countries, 95 produce coconuts, with the Philippines, Indonesia, and India producing about 70% of the world's total copra, the dried coconut kernel from which coconut oil is made [7]. Coconut oil is a readily accessible resource in these countries and most countries worldwide.

We plan to perform a blinded equivalence study to formally evaluate coconut oil as an alternative to commercially produced ultrasound gel by comparing the quality of ultrasound images using each respective coupling media. Additionally, we aimed to assess patients' satisfaction with the use of coconut oil for this purpose. This study will use organic refined coconut oil.

2.0 Objectives

2.1 Primary Objective

- To evaluate the quality of ultrasound images obtained using coconut oil compared with commercial ultrasound gel.

2.2 Secondary Objective

- To access patient acceptability of coconut oil as compared to commercial ultrasound gel.

3.0 Outcome Measures/Endpoints

3.1 Image Quality

- Paired images will be displayed side by side in random order and each of the following parameters will be assessed using a 10 cm visual analog scale by a blinded reader:
 - Resolution – sharpness/crispness of image, lack of haziness
 - Image detail – clarity of organ outlines and ease with which boundaries of structures are seen
 - Total image quality – contrast of solid and fluid-filled structures and absence of noise
 - Clarity/definition:
 - BPD/HC – thalami and CSP
 - Abdominal circumference – umbilical vein, portal sinus
 - FL - femur bow definition

3.2 Patient Acceptability

- A 10-question, 5-point Likert scale survey will be administered to all participants following their ultrasound with both coupling mediums to compare acceptability.
- See **Appendix 1** for patient survey.

4.0 Eligibility Criteria

[figure not shown]
4.1 Inclusion Criteria

- Singleton pregnancy
- Patients presenting for an anatomy or growth US
- Patients assigned to the pre-determined ultrasound suite that will stay constant throughout the study so that the same ultrasound machine is used to obtain all images.

4.2 Exclusion Criteria

- Allergy to coconut
- Active inflammatory dermatologic conditions (dermatitis, eczema, or psoriasis)
- Multiple gestation pregnancy

5.0 Study Design

6.0 Enrollment/Randomization

- 6.1 Patients assigned to have their anatomy or growth ultrasound at the Maternal Fetal Medicine clinic in the Riley Outpatient Center will be approached to participate after the patient is roomed in the ultrasound suite and while they are waiting for the ultrasound technician to begin the scan.
- 6.2 The patient will be randomized to either starting the exam by first obtaining the study images with coconut oil and then proceeding with the standard ultrasound using commercial ultrasound gel or starting with the scheduled ultrasound using the commercial ultrasound gel and ending by obtaining the study images using coconut oil.
- 6.3 The same ultrasound machine will be used to obtain all images in this study. This means that only patients assigned to have their imaging in the ultrasound suite with the “study ultrasound machine” will be included in the study.

7.0 Study Procedures

- 7.1 Recruitment and consent will take place in the ultrasound suite after the patient's vitals are collected and while they are waiting for the ultrasound technician to begin the ultrasound scan.
- 7.2 After the patient is consented and all questions are answered, the patient's information will be entered into a RedCap and they will be randomized to either starting the scan by first obtaining the required study images with coconut oil and then proceeding to the standard ultrasound using commercial ultrasound gel (Arm 1) or to starting with the scheduled ultrasound using the commercial ultrasound gel and ending by obtaining the required study images using coconut oil (Arm 2).

- 7.3 Whether assigned to Arm 1 or Arm 2, prior to the collection of the study images using coconut oil, the participant will be handed a small plastic cup with a pre-measured amount of coconut oil and they will be asked to warm it in their hand for at least 2 minutes. They will then apply the coconut oil to their own abdomen with their hands prior to the ultrasound technician obtaining the required images.
- 7.4 The ultrasound technician will collect 3 extra images for study purposes only using the coconut oil. This will only require 5-10 extra minutes of your time.
- 7.5 The ultrasound technician will drag the 3 fetal biometry images obtained with coconut oil and the 3 fetal biometry images obtained with commercial gel to the bottom of the set of images obtained throughout the study. They will label the images according to their randomization. For example, if randomized to coconut oil first followed by commercial gel, the coconut oil images will be labeled 1 and the commercial gel images labeled as 2. The images will be paired next to their counterpart.
- 7.6 While the images are being labeled and sorted, the patient will quickly fill out the short Patient Acceptability Survey.
- 7.7 The patient will be thanked for their participation and continue with the scheduled visit. A towel will be provided to clean off ultrasound gel or coconut oil as needed.

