11.0 Statistical Consideration

Study Design

There are 3 views for a given ultrasound, 2 raters will rate each image on 4 different factors, and each person will receive ultrasound using both types of medium (Coconut oil vs Commercial gel). Only image raters will be blinded to the medium used. Patients will be provided the two mediums in a different order (although the specific images will be in the same order). Quality will be estimated by two raters. Patient satisfaction with both mediums will be asked at the end of the ultrasound session and will ask patients how satisfied they were with each specific medium (Coconut oil vs Commercial gel) since they aren't blinded to type.

The study statistician will create a randomization list (A vs B) as to which medium each woman will receive first.

4 factors: Quality (Equivalence outcome), Resolution, Detail, Specific anatomic view (Based on a given image). All factors other than quality will be analyzed with a standard superiority hypothesis.

The primary hypothesis is that image quality (overall) will be equivalent between the two types of ultrasound medium. This will be tested using the within-patient contrast obtained from a linear mixed model.

Report Definitions

N is the number of items sampled from the population. Effect Size: $d = (\mu_1 - \mu_2) / \sigma$ is the effect size. Cohen recommended Low = 0.2, Medium = 0.5, and High = 0.8. σ is the assumed population standard deviation of the paired differences. Alpha is the probability of rejecting a true null hypothesis.

Our primary hypothesis for equivalence:

$$H_0: \delta \leq -10 \text{ or } \delta \geq 10 \text{ vs. } H_1: -10 < \delta < 10$$

With $N = 40$, an equivalence test of the mean difference in image quality (measured on 0 to 100 scale) from a paired design using two one-sided t-tests (which should provide similar power to the contrast from our model), achieves 83% power at .05 significance level when the actual paired difference is 5 and the estimated standard deviation of paired differences is 12 when equivalence limits are -10 and 10. For the continuous outcome of patient satisfaction, we will have 80% power to detect an $ES = 0.45$ with type I error set at .05 based on a paired t-test which provides similar power to the contrast from our model.

Statistical analysis

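### In both arms the gel images come from the clinical scan and the oil images are a study add-on, with no common rule for the study frame, so acquisition context is fully aliased with medium

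*Combined protocol and SAP*

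**What the plan says.** Only the order of the two media is randomised. Sections 6.2 and 7.2 describe two sequences. In Arm 1 the oil study images come first and the standard gel ultrasound follows. Arm 2 reverses this: "starting with the scheduled ultrasound using the commercial ultrasound gel and ending by obtaining the study images using coconut oil". In both, gel is the clinical examination and oil is the addition.

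Section 7.4 confirms the status of the oil images: "The ultrasound technician will collect 3 extra images for study purposes only using the coconut oil". It allots 5 to 10 further minutes. No corresponding step creates gel images for the study.

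Section 7.5 covers what happens after scanning: "The ultrasound technician will drag the 3 fetal biometry images obtained with coconut oil and the 3 fetal biometry images obtained with commercial gel". These go to the end of the image set, are numbered by order of use and are placed beside their counterparts. No rule says which frame counts if a view was saved more than once.

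On blinding, section 11.0 states: "Only image raters will be blinded to the medium used". The technician therefore knows the medium throughout. The primary model in section 11.0 has effects for view and medium and a random rater effect. Equivalence is concluded if the 90% confidence interval lies inside ±10.

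**The concern.** The primary contrast is meant to isolate the coupling medium. As written, it compares gel images from a clinical examination with oil images from a short research block. Time available, number of attempts, machine settings, fetal position and the technician's purpose could all differ between the two. Any such difference would follow the medium in every patient.

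The planned safeguards do not reach this:

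- **Randomised order** balances first-versus-second effects. It cannot balance something attached to the same medium in both arms.
- **Rater blinding** starts after the frames are fixed.
- **The mixed model** cannot adjust for a factor that takes one value for all gel images and another for all oil images.
- **A larger sample** would narrow the interval around a biased value without moving it.

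At stake is the equivalence conclusion in either direction. A bias that widens the difference could hide true equivalence, and one that narrows it could produce false equivalence.

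**Working it through.** **1. Aliasing, from the text**

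| | Arm 1 | Arm 2 |
|---|---|---|
| Oil images | three extra study images, first | three extra study images, last |
| Gel images | standard scan, second | scheduled scan, first |

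Order differs between the columns. Acquisition type does not: oil is always the add-on and gel always the clinical scan. An indicator for acquisition type would be identical to the indicator for medium, so no model fitted to these data can estimate the two separately.

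**2. The plan's own power figure**

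Inputs from section 11.0: N = 40, SD of paired differences 12, limits ±10, true difference δ = 5, one-sided level 0.05 for each test (matching the 90% interval), stated power 83%.

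SE = 12/√40 = 1.897.

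Normal approximation: Φ((10 − δ)/SE − 1.645) = Φ(5/1.897 − 1.645) = Φ(0.99) = 83.9%.

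Exact calculation: equivalence is declared when the sample mean difference D and sample SD S satisfy D + t·S/√40 < 10 and D − t·S/√40 > −10, with t the 95th percentile on 39 df. Integrating over the distribution of S gives 82.7%. The stated 83% reproduces.

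**3. Sensitivity to an assumed bias b**

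The documents give no size for an acquisition effect, so b is an assumption throughout. A bias moves the centre of the test from δ to δ + b, and the exact calculation is repeated there.

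| Assumed size of b (points) | True δ = 5, bias away from zero: power | True δ = 10, bias toward zero: false equivalence |
|---|---|---|
| 0 | 82.7% | 5.0% |
| 1 | 66.5% | 13.0% |
| 2 | 46.4% | 27.1% |
| 3 | 27.1% | 46.4% |

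The columns share values because the result depends only on δ + b. For example, 5 + 3 and 10 − 2 both equal 8, and both give 27.1%.

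The reverse direction also occurs. At δ = 5, a 2-point bias toward zero would raise power to 97.6%, since the test is then centred on 3.

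For scale, if the 10 cm analogue line in section 3.1 maps linearly onto 0 to 100, 2 points is 2/100 × 10 cm = 0.2 cm. The planning difference of 5 already uses half the margin, which is why small shifts matter.

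**The case against.** A reader might infer that several gel frames are saved per view and that the technician picks the best, or picks the one that matches the oil frame. The documents do not support this. Section 7.5 speaks of three images per medium, which most naturally means one per view, in line with the three views in section 11.0. The same dragging, labelling and pairing applies to both media, and pairing most plainly means placing the same view side by side. In Arm 2 the gel frames are captured before any oil image exists.

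A reader might also infer that gel receives more effort. That is not stated either. The only time given is the 5 to 10 minutes for oil, part of which may be the warming step in section 7.3. Dedicated research shots could receive more attention per image than routine biometry.

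The plan also has real controls: one machine, within-patient pairing, the same order of views, two raters, and blinded side-by-side reading in random order. Drawing gel images from usual care is a defensible pragmatic choice.

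All of this stands. It leaves the direction and size of any bias unknown, and it makes frame selection a possibility left open by the text, not something the text describes. It does not answer the aliasing, which follows from sections 6.2, 7.2 and 7.4 alone. None of the listed controls equalises how an image is obtained or which saved frame becomes the study image.

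**Conclusion.** The point holds as an uncontrolled source of bias, not a demonstrated one. Acquisition context is fully aliased with medium, and an unblinded technician extracts the frames without a written rule. Nothing in the randomisation, blinding or analysis could detect or remove a resulting bias afterwards.

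No stated number is wrong on this point. The sensitivity figures rest on the plan's N, SD and limits, on an assumed bias of 1 to 3 points, and on the paired t-test that the plan itself treats as close to its model contrast. The false-equivalence figures also assume a true difference exactly at the limit. They show that a small bias would matter, not that one is present. The change is worth making before enrolment because the primary conclusion depends on this contrast and the remedy is cheap.

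**What to change.** Amend sections 7.4 and 7.5 as follows.

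1. For each view and each medium, the study image is the first saved frame that the technician accepts as the standard biometry plane. It is flagged when saved and not replaced later.
2. Where the clinical scan allows, the three gel biometry views are taken as one block next to the oil block, in the same view order: at the start of the gel scan in Arm 1 and at its end in Arm 2.
3. The rest of the clinical scan is unchanged. Gel frames saved later are used for care only.

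A cap on time or attempts for the gel views is not needed for this and should be optional at most, because those views belong to a clinical examination.

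The cost is protocol wording and a short technician instruction. Section 7.5 already relies on gel biometry images, so no extra patients or gel views are required. There are small downsides: biometry is done at a set point in the scan, and the gel study frame may not be the best of the clinical scan. The unblinded technician still decides what to save, so the rule narrows the gap without closing it. That remainder should be reported as a limitation.

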Descriptive statistics of image outcomes of quality, resolution, and detail will be summarized overall and separately by medium. For the specific anatomic view, this will be estimated separately for each view by medium. For the primary outcome, a linear mixed model will be fit to quality, including effects for view and medium (Coconut oil vs Commercial gel and a random rater effect. To test the hypothesis, the within-person mean difference in image quality for Commercial gel vs Coconut oil will be estimated along with associated **90%** confidence interval. If the confidence interval is inside the equivalence region of [-10, 10], we will reject the null hypothesis and conclude Coconut oil is equivalent to Commercial gel with regard to quality.

For all other image outcomes, a similar model will be fit except the mean difference in the outcome between mediums and associated **95%** confidence interval will be reported as we do not a priori know which medium will be better. Therefore, we report standard superiority hypothesis with type I error set at 0.05. For the outcome of the specific anatomic view, the model will only be fit for that specific image, thus the model will not contain the effect of view. All models will be examined for fit.

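### No stated step removes the first coupling medium before the second is applied, and the primary model has no order term

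*Combined protocol and SAP*

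**What the plan says.** Every participant is scanned with both media in one visit. Arm 1 has the oil images first and then the scheduled gel scan. Arm 2 is the reverse, described in Section 6.2 as "starting with the scheduled ultrasound using the commercial ultrasound gel and ending by obtaining the study images using coconut oil". Order is randomised; Section 11 states "The study statistician will create a randomization list (A vs B) as to which medium each woman will receive first".

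Section 7.3 gives the steps before the oil images for both arms: the participant receives a cup of oil, warms it, and then "They will then apply the coconut oil to their own abdomen with their hands prior to the ultrasound technician obtaining the required images". Nothing is said there about gel already on the skin in Arm 2, and nothing in 7.2 covers oil on the skin before the gel scan in Arm 1. Sections 7.4 and 7.5 deal with collecting and labelling images. Section 7.6 has the survey: "While the images are being labeled and sorted, the patient will quickly fill out the short Patient Acceptability Survey". Cleaning appears only afterwards, in 7.7: "A towel will be provided to clean off ultrasound gel or coconut oil as needed".

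The primary model in Section 11 is described as "including effects for view and medium (Coconut oil vs Commercial gel and a random rater effect". No period, sequence or order term is listed. The planned equivalence test "achieves 83% power at .05 significance level when the actual paired difference is 5 and the estimated standard deviation of paired differences is 12", with limits of -10 and 10.

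**The concern.** Followed as written, the procedure allows the second medium's images to be taken through what is left of the first. The primary claim is equivalence, so the usual comfort that contamination is conservative does not apply. If second images come to resemble the first medium, the measured difference shrinks and equivalence is easier to declare.

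Randomised order protects the mean only against an effect that is the same in both sequences. The two sequences are not mirror images: in Arm 2 the oil follows a whole scheduled gel scan, while in Arm 1 the gel follows three oil images. Only the raters are blinded, so informal cleaning could differ between arms without anyone recording it.

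**Working it through.** **Inputs.** From Section 11: N = 40 pairs, SD of paired differences 12, limits ±10 on a 0 to 100 scale, 90% confidence interval inside the limits (one-sided 0.05 each), planned true difference 5. Assumed: 20 patients per order (the ratio is not stated), normal differences, and every residue size. As the plan itself does, the paired two one-sided tests stand in for the mixed-model contrast.

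**1. The plan's own figure.** Standard error = 12/√40 = 1.897. Critical t on 39 df = 1.685. Noncentrality = (10 − 5)/1.897 = 2.635. The noncentral t gives 82.7% power, against 83% stated, so it reproduces. At a true difference of 10 the chance of declaring equivalence is 5.0%.

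**2. How residue enters the contrast.** Let δ be the true gel-minus-oil difference, *a* the points that oil residue adds to gel images (Arm 1), and *b* the points that gel residue adds to oil images (Arm 2). Negative values mean degradation.

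- Arm 1 difference: δ + a. Arm 2 difference: δ − b.
- Mean with 20 per arm: δ + (a − b)/2.
- *Equal effects*, a = b = c: the mean is δ. The arms sit at δ + c and δ − c, so without an order term the estimated SD rises to about √(144 + 40c²/39), which is 12.2, 13.0 or 15.7 for a c of 2, 5 or 10 points.
- *Unequal effects*: the mean shifts by half of (a − b), up or down. An order term leaves this estimate unchanged in a balanced design.
- *Attenuation*, where second images lose a fraction f of the difference: a = −fδ and b = +fδ, so the mean is (1 − f)δ. Again an order term changes nothing.

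**3. Results.** Percentage of trials declaring equivalence, without / with an order term (39 / 38 df). The first row and the attenuation rows are by exact calculation; the others are from 400,000 simulated trials.

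| Assumed residue | True difference 5 (power) | True difference 10 (error) |
|---|---|---|
| None | 82.7 / 82.7 | 5.0 / 5.0 |
| Second medium 2 points worse, both sequences | 82.2 / 82.8 | 4.7 / 5.0 |
| Second medium 5 points worse, both sequences | 78.9 / 82.8 | 3.7 / 5.0 |
| Second medium 10 points worse, both sequences | 66.6 / 82.7 | 1.6 / 5.0 |
| 10% attenuation, both sequences | 88.6 / 88.5 | 13.0 / 13.0 |
| 20% attenuation, both sequences | 92.8 / 92.8 | 27.1 / 27.1 |
| Oil after gel only, 4 points worse | 45.4 / 46.4 | 0.3 / 0.4 |
| Gel after oil only, 4 points worse | 97.5 / 97.6 | 26.4 / 27.2 |

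In the last two rows gel is truly the better medium. At a true difference of 5, equivalence is the correct answer, so the higher percentages there are not errors.

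The order term recovers the power lost to equal degradation. It does nothing for attenuation or for one-sequence residue.

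**The case against.** Five arguments deserve weight.

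*The step may exist.* Section 5.0 is a bare heading in the available text, and the Study Schema listed in the contents does not appear. A reader might infer that the plan as a whole omits a removal step. The documents do not support that; only its absence from 7.2 to 7.5 can be asserted.

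*Cleaning probably happens.* The survey asks how easily the gel came off, and it is filled in at 7.6, before the towel is mentioned at 7.7. The towel item is therefore probably not chronological, and wiping gel off before oil in Arm 2 is a natural reading. This stands as inference, but it does not settle Arm 1, and nothing requires or records cleaning between media.

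*The direction is unknown.* A reader might infer that residue biases this trial towards equivalence. That follows for attenuation only. Residue could have no effect, could improve coupling, or could act unequally in both sequences. The same 4 points can raise or lower both power and error, as the table shows.

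*The order term matters little for small effects.* At 2 points it is worth about half a percentage point of power, and no document supports residue of 5 or 10 points. This stands, but the term costs one degree of freedom and leaves planned power at 82.7%.

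*Wiping has a price.* It may not remove all the oil. In Arm 1 it would take the oil off before patients rate how it rubs in and how their skin feels (oil items 3 and 4), which touches the secondary objective. This stands and shapes the fix.

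**Conclusion.** The point holds as a gap in the written procedure and the model, not as an arithmetic error. The stated 83% power is correct if residue has no effect.

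Under the assumed residue sizes, false equivalence at a true difference of 10 goes from 5% to 13% or 27% with 10% or 20% attenuation. A 4-point effect in one sequence takes power at 5 from 83% to 45–46% or to 97–98%, and error at 10 from 5% to 0.3–0.4% or to 26–27%, depending on the sequence. Equal degradation of 2, 5 or 10 points cuts power to about 82%, 79% or 67% without an order term and leaves it at about 83% with one. None of these is a forecast, since the documents give no residue size, and the 20/20 split is assumed. The change is worth making because it is cheap; confidence that residue matters in practice is only moderate. A removal step in Section 5.0 or the Study Schema would answer the procedural half of the point.

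**What to change.** (a) In the primary model in Section 11, add order (whether the medium was used first or second) as a fixed effect. State that it recovers power lost to equal residue but does not correct attenuation or unequal residue. Cost: one degree of freedom.

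(b) In 7.2 and 7.3, state that in both arms the abdomen and probe are wiped of the first medium before the second is applied, and record completion in RedCap. This reduces residue but may not eliminate it. Cost: about a minute per visit (assumed) and one data field; a towel is already supplied. If Section 5.0 or the Study Schema already contains such a step, carry it into Section 7.

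(c) Because (b) removes the oil before the survey in Arm 1, show oil survey items 3 and 4 by arm as a descriptive supplement and keep the overall paired comparison as planned. With about 20 patients per arm, the effect size detectable with 80% power within an arm is about 0.66, against 0.45 for all 40, so the by-arm display should not carry a formal test.
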